### **Participant Compensation.**

Following randomization, participants will be remunerated up to \$988 plus parking vouchers or metro cards (if available) for completing all visits and assessments from baseline/screening through the end of the study. This includes up to \$378 for completion of all EMA assessments, up to \$300 in compliance bonuses, and up to \$40 for at-home urine collection (up to \$30 for in-person visits and up to \$40 for virtual visits) and a \$30 return phone bonus for returning their study phone in working order (including the accessories that were issued with the phone like charger, cord, case and screen protector, etc.). In an effort to reduce clinic burden, when the Ver 7 revision is approved, We will begin sending questionnaire links to participants in advance of their in-person scheduled clinic visits and offering a \$10 bonus (\$50

total max) if they complete electronically prior to coming in to the clinic visit. If the visits are conducted virtually, participants will be offered a \$10 bonus (\$40 total max) for providing saliva/cheek swab samples. The current compensation scheme has been adjusted accordingly and will only affect newly consented participants after the revision is approved (this includes those newly consented with phone bonus revision as well). Those that already signed consent under the previous scheme will be compensated according to the previous scheme. See Appendix Y. for the Compensation Schedule. Participants will receive their monetary compensation in the form of a reloadable Bank of America card that is issued to them at the baseline screening visit and reloaded at subsequently completed visits (see Appendix D).

### **Medication Blinding**

The blinding will be handled by the Tobacco Research and Treatment Program's database management team. The master key linking the actual treatments with the blinded codes will be maintained by the database team. The database team will write and maintain the software that conducts the randomization of research participants, including the minimization procedure being used for subject stratification and random assignment. Study staff randomize the study participant after all eligibility criteria are met and recorded in the database (by design the program will not work otherwise). The group assignment is displayed to study staff who assigned the medication as blinded code. Blinded reports are available that provide information on the distribution of factors within treatment group as a cross check on the program's accuracy. Study team members (data managers and senior staff) not involved in direct subject care will have access to randomization assignments. We have implemented this process in several other protocols.

### **Breaking the Blind**

Un-blinding of single cases by the investigator will only be performed if relevant for the safety of the participant. The PI along with the Program Director (PD) will be responsible for implementing procedures for maintaining the blind and for breaking the blind when necessary. The PI must notify the IND Medical Monitor/Office prior to the un-blinding of a participant. In emergency situations, the Principal Investigator (PI) would consult with the Program Director (PD) and/or the research team's Data Management Supervisor (DMS) to obtain immediate blinding information for the participant. The PD/DMS would then pass this information on to the PI to enable the participant to be treated. In non-emergency situations, the same procedures would apply, however the PI and PD will discuss and evaluate the request, then, the PI after consulting with the study physician would be responsible for making the decision of whether or not to un-blind. When the blinding code is broken, the reason will be fully documented and included on the appropriate data collection forms. After a subject completes the study, they can be provided with their medication assignment(s) if requested.

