participant is experiencing sooner rather than the next scheduled contact, which is approximately 21 days after the visit. Participants are asked to bring all VLNCC products back at each visit whether opened or unopened for purposes of accounting (see Appendix KK).

The VLNCCs are made from genetically engineered tobacco strains that vary in nicotine content and are produced by RTI International (Research Triangle Park, NC), under NIDA contract (NOT-DA-14-004). As noted earlier, the VLNCC dosage, 0.03 mg, was selected from a multisite FDA-sponsored TCORS (U54DA031659 Project 1; PIs: [name] & [name]) designed to identify a dosage that was minimally reinforcing yet acceptable to smokers.

**COVID-19 adaptation:** Participants will be mailed their 3-week allotment of VLNCCs prior to the start of this phase.

**Phases 3 & 4: VLNCC+ECIG (weeks 5-7, 8-10).** During Phases 3 & 4, participants will be provided with the same weekly allocation of VLNCCs as in phase 2, as well as a supply of e-cigs. During these phases, participants will be encouraged to freely use any combination of the VLNCCs and their assigned ECIG product, ECIG-Hi or ECIG-Lo, randomized within-subjects by phase (i.e., Phase 3: ECIG-Hi, Phase 4: ECIG-Lo; or Phase 3: ECIG-Lo, Phase 4: ECIG-Hi). Those assigned to the eGo ECIG arm will receive 2 eGo LCD batteries (1100 mA; 3.3V battery) with puff counter and charge level display, 1 e-cig Universal AC-USB Adapter, 1 USB recharger, a 3 week supply (21 days) of 510 XL Dual Coil Cartomizers (1.5 Ω), a user manual, and a carrying pouch at the beginning of phases 3 and 4. The ECIG-Hi and ECIG-Lo cartomizers will contain 1 ml of 36 mg/ml or 8 mg/ml nicotine solution, respectively, in the flavor (tobacco, fruit, cream, or menthol) of each participant's choice.

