Participants randomized to the JUUL arm will be provided with the same weekly allocation of VLNCCs as in phase 2, as well as a supply of JUUL e-cigs. During these phases, participants will be encouraged to freely use any combination of the VLNCCs and their assigned JUUL product, JUUL-Hi or JUUL-Lo, randomized within-subjects by phase (i.e., Phase 3: JUUL-Hi, Phase 4: JUUL-Lo; or Phase 3: JUUL-Lo, Phase 4: JUUL-Hi). Each participant will receive JUUL Device Kits (2 rechargeable JUUL devices and 2 USB chargers), a supply of JUULpods to last to the next laboratory session (one pod/day), and a user manual. The JUUL-Hi and JUUL-Lo JUULpod cartomizers will contain 1 ml of 59 mg/ml or 36 mg/ml nicotine solution, respectively, in the flavor (tobacco or menthol) of each participant's choice.

At the beginning Phase 3, participants will receive training in how to use the ECIG product. They will participate in hands-on training that will include e-cig assembly (battery and cartomizer), turning the cartomizer on and off, puffing, and recharging the battery. The training session will include a minimum of three bouts of 10 puffs each in which the user will be encouraged to vary puff topography to maximize desired sensory qualities of product use. Participants will be able to try and choose from tobacco, fruit, cream, or menthol flavored nicotine solutions (see Appendix JJ). This procedure is similar to what is used in the P50 TCORS led by our co-investigator [name]. A check-up call may be conducted around 3 days after the start of Phase 3 to troubleshoot any problems the participant may have in terms of starting a new study product. Participants are asked to bring all ECIG products back at each applicable visit whether used or unused for purposes of accounting (see Appendix LL).

Participants and study staff will be blind to ECIG nicotine dose condition. The eGo cartomizers will be shipped from the vendor to the study Program Director at MD Anderson and then taken over to Greenpark Pharmacy or will be shipped directly to Greenpark, who will fill them with the appropriate volume, concentration, and flavor of nicotine solution. Senior staff that are unblinded (i.e. do not have direct patient contact) will store and manage the inventory and labeling of blinded products. Study staff will distribute the product to patients at each visit. The nicotine solution will be procured through AVAIL Vapor, LLC and shipped to the study Program

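### Completers can learn their dose order on request while others are still on study, and nothing stated protects the blind for later participants

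*Combined protocol and SAP*

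**What the plan says.** The Procedures section promises a double blind on dose: "Participants and study staff will be blind to ECIG nicotine dose condition". Within the eGo arm there are two sequences, "Phase 3: ECIG-Hi, Phase 4: ECIG-Lo; or Phase 3: ECIG-Lo, Phase 4: ECIG-Hi", and the JUUL arm has the same two-sequence structure with its own doses.

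Medication Blinding describes how the codes work. "The master key linking the actual treatments with the blinded codes will be maintained by the database team". At randomisation, "The group assignment is displayed to study staff who assigned the medication as blinded code". On access, "Study team members (data managers and senior staff) not involved in direct subject care will have access to randomization assignments".

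Breaking the Blind opens with a safety restriction, "Un-blinding of single cases by the investigator will only be performed if relevant for the safety of the participant", and sets out emergency and non-emergency routes. It closes with a separate permission: "After a subject completes the study, they can be provided with their medication assignment(s) if requested". That permission depends on the individual's own completion. Neither this section nor any other ties it to the last participant's follow-up or to database lock. Nor does the protocol say who makes the disclosure or whether staff with participant contact are kept out of it.

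**The concern.** ECIG-Hi against ECIG-Lo is the Aim 1 hypothesis and the comparison that the dose blind protects. A disclosure made after one person finishes cannot alter that person's treatment-phase data. The question is what it reveals about people still on study or not yet enrolled. If contact staff see a code that means the same thing for everyone who carries it, learning one participant's order teaches them the code.

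The consequences would fall where staff knowledge can enter the data or the safety record. Cigarettes per day, one of the two primary measures, is self-reported, with a timeline follow-back interview by research assistants as back-up. Staff also give device training at the start of Phase 3 and may make a check-up call about three days later. The principal investigator or a physician attributes adverse events.

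**Working it through.** The plan gives no figure to reproduce here. The check compares the relevant sections and uses simple arithmetic for the overlap.

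**1. Do completers coexist with later participants?** The inputs are the enrolment ceiling of 380 (Participants), and 176 exposed with 77% retention to the end of study at the unplanned adverse-event look (Potential Problems & Alternative Strategies).

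- Still to come at that look: 380 − 176 = 204 at most, and 204 / 380 = 53.7%.
- Completers able to ask by then: 0.77 × 176 = 135.5, about 136. This is approximate, because some of the 176 may still have been on study.

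So the permission operates while a large part of the trial may still be ahead. The 204 spans both device arms. A code learned in one arm need not apply in the other, so a single disclosure would reach fewer than 204.

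**2. Are the codes shared across participants?** The documents do not say. Three statements in Medication Blinding lean towards sharing. The master key links codes to treatments, not to participants. What staff see is described as the group assignment in coded form. And "Blinded reports are available that provide information on the distribution of factors within treatment group", which requires group-level labels of some kind. Pointing the other way, the study product accountability plan puts the subject ID into the JUUL pod code. That code also carries a nicotine-strength element, which would itself be decodable if it is constant across participants.

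**3. What would one disclosure reveal?** With two orders per arm, identifying the code for one order leaves 2 − 1 = 1 other, so both are known.

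| Codes shown to contact staff | Disclosed dose reaches contact staff | Whose order those staff can decode |
|---|---|---|
| Reused across participants | Yes | The requester and every later participant in that arm |
| Reused across participants | No | Nobody |
| Participant-specific | Yes | The requester only |
| Participant-specific | No | Nobody |

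Only the first row harms the trial more widely, and it needs both conditions.

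**4. Could the dose reach people who should be blind?** Unblinded staff without participant contact exist and could make the disclosure, but no section requires that they do. In the emergency route described in Breaking the Blind, the program director or data management supervisor passes the assignment to the principal investigator. Non-emergency requests follow the same procedures, with the investigator deciding. Whether a completer's request goes this way is not stated. If it does, it informs someone who may also attribute adverse events.

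**5. Which outcomes are exposed?** The primary source for cigarettes per day is the participant's own smartphone diary, and the interview supplements missing data. Staff knowledge could therefore act through those interviews, participant contacts and adverse-event attribution. TNE is a laboratory assay, so its measurement is less exposed.

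**The case against.** The strongest reply is that the documents describe a separation of roles that may already contain the risk. The database team holds the key, and those with access to assignments have no direct care role. Unblinded senior staff also handle product labelling, and at least the JUUL pods carry the subject ID. This stands as a reason not to claim that the blind is broken. It does not close the gap, because the protocol neither assigns the disclosure to those staff nor says that the codes are unique.

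The bias pathway is also narrow. Current participants are not unblinded by someone else's disclosure, and only one person per household may enrol. Device training is described once, at the start of Phase 3, and no check-up call is scheduled at the switch to Phase 4. These points limit the likely size of any bias and are accepted.

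Four stronger readings are tempting, and the documents do not support them.

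- A reader might infer that the first and last sentences of Breaking the Blind contradict each other. The first governs unblinding by the investigator, while the last concerns informing someone who has finished. They can coexist, though the section should say how.
- A reader might infer that disclosure can precede the 30-day call, at which open adverse events and product use are reviewed. Completion is not defined. Table 4 lists that call at Day 101, after the final visit on Day 71, so completion may well include it.
- A reader might infer that staff who knew the codes could predict the next minimised assignment. The balance reports are described as blinded. Their recipients, the factors used and any random element are not given. Everyone in an arm receives both doses, so foresight would not let staff steer anyone to a single dose.
- A reader might count every expected completer as a potential leak. The documents give no request rate, and nobody remains to be decoded after the last completers.

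**Conclusion.** The point holds as an uncontrolled risk to the blind, not as demonstrated unblinding. The protocol allows disclosure on individual completion during a trial with rolling enrolment, and it states no safeguard for those who follow.

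The size is a range. At one end, with reused codes and disclosure reaching contact staff, one disclosure decodes the Phase 3 and Phase 4 dose of every later participant in that arm. At the other, with participant-specific codes, only the requester is decoded and later participants are unaffected. The text leans towards reused codes but does not settle it, and it is silent on whether the dose reaches contact staff. The figures of up to 204 participants still to come and about 136 completers at the adverse-event look show overlap. They do not measure bias.

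Any effect would fall mainly on the interview back-up for cigarettes per day, on participant contacts and on adverse-event attribution, and less on TNE. The change is worth making because it amends a stated rule at little cost.

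**What to change.** Replace the last sentence of Breaking the Blind with wording to this effect: *Participants may be told their assignment on request only after the last participant has finished the 30-day follow-up and the database has been locked. Unblinding for safety, as described above, is unchanged.* This also settles how the closing permission fits with the section's opening restriction.

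In Medication Blinding, confirm that the codes shown to contact staff are participant-specific, or make them so. If they already are, one sentence saying so is enough.

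The main cost is that participants wait longer to learn their assignment. If codes are currently shared, the randomisation display would also need changing. The documents give no basis for estimating that effort, but the software is written and maintained by the program's own database team.

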### **Potential Risks**

#### ***Adverse Experiences Associated with Physiological Assessments***

Participants may also experience potential tobacco withdrawal effects (e.g., increased irritability, difficulty concentrating, etc.) during VLNC usage. None of these effects typically result in serious adverse health consequences.

#### ***Adverse Experiences Associated Questionnaires***

It is unlikely that completing questionnaires would lead to any potential risks for participants, although some participants may be uncomfortable answering certain questions. To the extent these are required for study participation (i.e. psychiatric and medical history), patients who do not wish to answer will not be eligible for participation. It is highly unlikely that any legal, social, or psychological problems will result from this research. In the event a

participant experiences a mental health emergency (e.g. suicidality, etc.) procedures outlined in the Mental Health Procedures (Appendix Z) will be observed.

### **Adverse experiences associated with lung spirometry**

Spirometry is a forced expiratory assessment that is generally safe. The most common adverse experience is dizziness, the incidence of which would cause the procedure to be paused, per guidelines [124]. However, spirometry does acutely increase blood and thoracic pressure, and is contraindicated for myocardial infarct, pulmonary embolism, ascending aortic aneurysm, and recent major thoracic, abdominal, or head surgery [170]. Participants will be screened for these conditions and may be disqualified from pulmonary function testing if they have a history of any of these conditions. Severe adverse events are not expected for spirometry, but in rare circumstances, this can cause syncope or near syncope.

### ***Adverse Experiences Associated with Nicotine Abstinence/Withdrawal***

Participants may experience nicotine abstinence/withdrawal effects. These effects may include irritability, difficulty concentrating, insomnia, anxiety, dysphoria, and increased hunger. None of these effects result in serious adverse health consequences.

### ***Adverse Experiences Associated with VLNC cigarettes***

The cigarettes used in this study have been used in previous studies including the ongoing U54 discussed in preliminary studies, with no untoward adverse effects or significant increase in expired CO and other toxicants [28, 31]. All participants will undergo a review of their medical history prior to randomization and will be monitored throughout the study for potential adverse events. Potential side effects with VLNC cigarettes are similar to what might be expected from smoking their own cigarettes which have long term health consequences that are not enhanced by the short term use of VLNC cigarettes in this study. Compensatory smoking may occur which could lead to increased toxicant exposure, although in our current trial and in previous studies compensatory smoking was shown to be minimal and higher levels of toxicant exposure were generally not observed [28, 29, 31]. While 6 subjects in our interim analysis showed a CO >50 ppm, none were on the .03 mg/ml dose used here. Nevertheless we will follow the guidelines developed for the U54 for reporting adverse events for an increase in carbon monoxide levels. An adverse event will be reported if the CO is greater than 60 ppm for participants with baseline CO of less than 35. An average two CO readings of 100 ppm or greater will result in automatic withdrawal.

### ***Adverse Experiences Associated with e-cigarettes***

The short and long-term risks of using e-cigarettes are currently unknown. The most common side effects are changes in taste, dehydration, mucus in the throat/sinus, dry mouth, dry cough, throat irritation, sore throat, mouth ulcers, dizziness, headache, and nausea. However, it is possible that e-cigarettes may cause lung injuries or other serious health problems, as indicated by recent alerts by the CDC [81] and the Texas Department of State Health Services [84]. Some people who use e-cigarettes have reported experiencing seizures. Some of these individuals reported a prior history of seizures or using other substances at the same time as their e-cigarette. In addition, in many cases e-cigarette use has led to respiratory illnesses such as difficulties breathing, shortness of breath and/or chest pain before hospitalization. In some cases, e-cigarette use has led to death, possibly due to lipid pneumonia, and the CDC has advised people to stop vaping. In some cases, symptoms of mild to moderate gastrointestinal illness such as vomiting, diarrhea, or fevers or fatigue have been reported. We will inform study participants of these risks and that they should monitor yourself for symptoms (e.g., cough, shortness of breath, chest pain) and promptly contact the study staff they are experiencing such symptoms. We will also inform participants to call 911 if they are experiencing a potentially life-threatening emergency.

E-cigarettes may also increase nicotine dependence. If stored improperly (e.g., in a pocket or where the device can turn on accidentally), overheating of the device may occur, which presents a minor burn risk.

Study medical monitor [name] and his team will monitor for respiratory and other adverse events, along with our collaborator from the Department of Pulmonology, [name]. The study team will receive email updates about the vaping-related lung injury epidemic from the CDC and the Texas Department of State Health Services (see Appendix XX for examples of these updates). However, it should be noted that The Texas Department of State Health Services (DHS) weekly update on 2/10/2020 [84] stated that the "CDC is discontinuing data collection on February 18, 2020" concerning lung injury related to e-cigarette use. The final CDC report strongly linked the EVALI illness to THC cartridges that were adulterated with vitamin E acetate [85]. Regardless, the study coordinator (or designee) and [name] will continue to receive and review the Texas DHS and CDC alerts as long as they are published throughout the duration of this protocol. In the event of a new health risk associated with the electronic cigarettes used in this protocol that is identified by these weekly alerts, we will take the following steps: (1) the newly identified risk will be discussed within 5 days by study chair [name], collaborator and Study Physician [name], pulmonology collaborator [name], and collaborator [name] to determine its relevance to the study products used in this protocol; (2) if the risk is deemed by the collaborators to be related to the study products used in this protocol, we will contact all active subjects by phone within 5 days and submit a PI memo to MD Anderson's IRB and IND offices that describes this new health risk (also within 5 days); (3) Upon determination by the IRB, the protocol and ICD will be revised to incorporate information about the newly identified risk, the DSMB will be informed at the next semi-annual review of this protocol, and active participants will be reconsented with the details of these new risks. We will keep a log of any new risks communicated by the CDC and/or the Texas HHS that are deemed relevant to the study products used in this protocol, including participants who are contacted and/or reconsented and the date of this contact. Note that CDC and Texas HHS monitoring of vaping-related lung injuries ended in February 2020.

